#### 9.6 Evaluability for Pharmacokinetic Analysis

Any patient who is enrolled, participates in the PK study, and receives the full dose of XL184 on Cycle 1 Day 1 will be considered evaluable for PK analysis provided that the patient completes Cycle 1 Day 1 sample collection.

Because PK can be evaluated in many different ways depending on how PK parameters are presented, the statistical analysis of the PK studies will proceed as follows:

- 1) A descriptive analysis of the pharmacokinetic parameters of cabozantinib will be performed to define Day 1 systemic exposure. Parameters to be collected are: AUC (0-24h),  $C_{max}$ ,  $T_{max}$ , and accumulation (the concentration before the dose on Day 22 divided by the concentration 24 hours after the Day 1 dose). The PK parameters will be summarized with the following summary statistics: mean, median, range, and standard deviations (numbers and distribution permitting).
- 2) The PK data in this study will be combined with the PK data from ADVL1211 for a population PK analysis to evaluate the effect of age on the clearance of XL184. The effect of age will be analyzed using the likelihood ratio test as implemented in the program NONMEM.

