### 4.1 Overview of Treatment Plan

Open label two-stage single arm study, with XL184 administered at 40 mg/m^2/day (cumulative weekly dose of 280 mg/m^2) on a continuous dosing schedule (one cycle = 28 days). Based on patients' BSA, there may be days that the dose will not be administered. The weekly dosing schedule can be found in [Appendix IV](#). Dosing will be performed based on body surface area (BSA), and rounded to the nearest 20 mg using a dosing nomogram (see [Appendix IV](#)). Treatment will continue until tumor progression or unacceptable toxicity.

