##### **XL184: PO**

Days: 1-28

Dose: 40 mg/m^2/day

Dosing will be performed based on body surface area (BSA), and rounded to the nearest 20 mg using the dosing nomogram (see [Appendix IV](#)). The cumulative weekly dose is 280 mg/m^2. Treatment will continue until tumor progression or unacceptable toxicity.

XL184 will be administered orally at approximately the same time each day.

Drug doses should be adjusted based on the BSA calculated from height and actual body weight measured within 7 days prior to the beginning of each cycle, and according to the dosing nomogram (see [Appendix IV](#)). Sites will fill out the number of prescribed tablets per day in the patient diary (see [Appendix III](#)). Patients must complete the patient diary with the date, time and number of XL184 tablets taken each day. The patient diary should be reviewed every 2 weeks during Cycle 1.

If a patient vomits after the dose of XL184 is administered, the dose should not be repeated. The tablet should be taken with a large glass of water on an empty stomach, and patient should not eat 2 hours before or 1 hour after each dose of XL184. The tablet should not be crushed or broken. Furthermore, a missed dose should not be taken within 12 hours of the next dose.

Patients should not eat grapefruit or drink grapefruit juice while being treated with XL184.

A note should be made in the patient diary if any of the above events take place.

See [Section 5.0](#) for Dose Modifications based on Toxicities.

Following completion of cycle, the next cycle starts on Day 29 or when starting criteria are met (see [Section 3.2.7](#)), whichever occurs later.

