**APPENDIX IV: XL184 DOSING NOMOGRAM**

**If a patient's dose is reduced due to toxicity, any future XL184 total weekly dose should not exceed a previously un-tolerated dose.**

See [Section 5.11](#) for the XL184 dose reduction table.

XL184 (Cabozantinib)	
40 mg/m^2/day	
BSA (m^2)	Weekly Dose/ Schedule for Initial Dosing
0.35 – 0.39	100 mg = 20 mg M, W, Th, Sat, Sun (or Day 1, 3, 4, 6, 7 of each week)
0.40 – 0.45	120 mg = 20 mg M, T, W, F, Sat, Sun (or Day 1, 2, 3, 5, 6, 7 of each week)
0.46 – 0.55	140 mg = 20 mg Daily
0.56 – 0.64	160 mg = 40 mg M, W, F, Sun (or Day 1, 3, 5, 7 of each week)
0.65 – 0.78	200 mg = 40 mg M, W, Th, Sat, Sun (or Day 1, 3, 4, 6, 7 of each week)
0.79 – 0.90	240 mg = 40 mg M, T, W, F, Sat, Sun (or Day 1, 2, 3, 5, 6, 7 of each week)
0.91 – 1.09	280 mg = 40 mg Daily
1.10 – 1.17	300 mg = 60 mg M, W, Th, Sat, Sun (or Day 1, 3, 4, 6, 7 of each week)
1.18 – 1.36	360 mg = 60 mg M, T, W, F, Sat, Sun (or Day 1, 2, 3, 5, 6, 7 of each week)
1.37 – 1.65	420 mg = 60 mg Daily
1.66 – 1.85	480 mg = 80 mg M, T, W, F, Sat, Sun (or Day 1, 2, 3, 5, 6, 7 of each week)
1.86 – 2.07	560 mg = 80 mg Daily
≥ 2.08	600 mg = 100 mg M, T, W, F, Sat, Sun (or Day 1, 2, 3, 5, 6, 7 of each week)

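### The Section 9.6(1) descriptive PK summaries take no account of Day 1 dose or weekly schedule, so they depend in part on the patient's BSA band

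*Combined protocol and SAP*

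**What the plan says.** Section 9.6 has two analysis items. Item 1 is descriptive: "A descriptive analysis of the pharmacokinetic parameters of cabozantinib will be performed to define Day 1 systemic exposure". The parameters are AUC(0-24h), Cmax, Tmax and accumulation, the last defined as "the concentration before the dose on Day 22 divided by the concentration 24 hours after the Day 1 dose". They are summarised by mean, median, range and standard deviation, as numbers and distribution allow. No dose normalisation is stated, and no grouping by dose, BSA band or schedule. Item 2 is a population PK model, combined with the phase 1 data, that tests age on clearance. Section 9.8 separately compares clearance in children under 9 with phase 1 by an equivalence test.

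The treatment sections fix a weekly total: "The cumulative weekly dose is 280 mg/m 2". Section 4.1 adds: "Based on patients' BSA, there may be days that the dose will not be administered". In Appendix IV the 0.46–0.55 m² band receives "140 mg = 20 mg Daily", and the next band, 0.56–0.64 m², receives "160 mg = 40 mg M, W, F, Sun (or Day 1, 3, 5, 7 of each week" (as printed, the parenthesis then closes). Section 7.2.1 recognises skipped days, but only in asking that the Day 22 sample (±2 days) fall on a dosing day.

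**The concern.** The nomogram controls the weekly dose, not the dose on Day 1. Two children whose BSA differs by 0.01 m² can start on Day 1 doses that differ about two-fold per m². An unscaled Day 1 mean then describes no single dose level.

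The accumulation ratio has a different problem. Under linear kinetics the size of the tablet dose cancels, but the number and timing of doses before Day 22 do not. Patients with the same kinetics have different expected ratios according to schedule.

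The extra sampling is justified in Sections 2.4.2 and 2.6 by the variable phase 1 PK and by interest in age groups, and PK is mandatory for the first 18 children under 9. BSA rises with age, so a table split or read by age could show a dosing pattern as though it were a difference in exposure or accumulation. It would also add to the reported spread.

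**Working it through.** **1. The plan's own figure.** In all 13 Appendix IV bands, tablet dose × dosing days equals the printed weekly dose. Divided by BSA at the band edges this gives 250 to 308 mg/m² a week. At the midpoints of the 12 closed bands it gives 264 to 285, mean 277. The stated 280 mg/m² is reproduced.

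**2. Day 1 dose per m²** (Day 1 dose ÷ BSA at band edges):

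| BSA (m²) | Dose on a dosing day | Days/week | Day 1 mg/m² |
|---|---|---|---|
| 0.46–0.55 | 20 mg | 7 | 36.4–43.5 |
| 0.56–0.64 | 40 mg | 4 | 62.5–71.4 |
| 0.65–0.78 | 40 mg | 5 | 51.3–61.5 |
| 0.79–0.90 | 40 mg | 6 | 44.4–50.6 |
| 0.91–1.09 | 40 mg | 7 | 36.7–44.0 |
| 1.37–1.65 | 60 mg | 7 | 36.4–43.8 |

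The extremes are 20/0.55 = 36.4 and 40/0.56 = 71.4, a ratio of 1.96. Without the 4-day band the range is 36.4 to 61.5, a ratio of 1.69.

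**3. Expected accumulation ratio.** Inputs: half-life 66.2 h (Section 2.4.2), Appendix IV day patterns, linear one-compartment superposition, Day 1 at the start of the pattern (so Day 21 is dosed).

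Let q = exp(−24 ln 2/66.2) = 0.778. The ratio is the sum of q^(21−d) over dosed days d = 1 to 21. This equals the sum over one week, W = Σ q^(7−x) for pattern days x, times (1 + q⁷ + q¹⁴) = 1.202.

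- 7 days: W = 3.725, ratio 4.48
- 6 days: W = 3.255, ratio 3.91 (13% below daily)
- 5 days: W = 2.836, ratio 3.41 (24% below)
- 4 days: W = 1 + q² + q⁴ + q⁶ = 2.192, ratio 2.63 (41% below)

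Over half-lives of 37.8 to 99 h (values in Sections 2.3.2 and 2.4.2) the 4-day ratio is 38% to 42% below daily: 1.74 v 2.81 at 37.8 h, 3.64 v 6.28 at 99 h.

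**4. Timing of the last dose.** Appendix IV also allows weekday schedules. On Monday/Wednesday/Friday/Sunday with a Wednesday start, Day 21 is not dosed and the last dose is 48 h before Day 22. Then W = q + q² + q⁴ + q⁶ = 1.970, and 1.970 × 1.202 = 2.37 rather than 2.63. By start day, the Day 22 ratio runs from 2.11 to 2.63 on the 4-day schedule and from 3.28 to 4.14 on the 6-day schedule. The ±2-day window has a similar effect: with Day 1 at the start of the 4-day pattern, a Day 21 draw gives 2.10.

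**5. Size against patient variability.** The documents give no BSA distribution. Assume BSA uniform over 0.5–1.1 m² and dose-proportional exposure. The mean Day 1 dose is then about 49 mg/m² with CV 20.5%. Taking the phase 1 AUC CV of 37% at 40 mg/m² as patient variability, total CV² = (1 + 0.205²)(1 + 0.37²) − 1 = 0.185. The dose share of log-AUC variance is ln(1.042)/ln(1.185) ≈ 24%. Other ranges tried for small children give 19% to 23%; 0.9–2.0 m² gives 7%.

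**The case against.** Four points can be made on the other side.

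- **Item 1 drives no decision.** The age question goes to clearance, in the population model and in the Section 9.8 equivalence test, and clearance takes the dose into account. This stands. A reader might infer that the equivalence conclusion or the age effect is biased; the documents do not support that.
- **Dose proportionality is open.** Section 2.4.2 reports similar steady-state AUC and Cmax over 30 to 55 mg/m² (mean AUC 32216, 30010 and 38101 h·ng/ml, with 6, 16 and 10 patients). Section 2.3.2 reports proportionality in adults. If exposure rises less than proportionally, dividing by mg/m² would make children with a high Day 1 dose look under-exposed. This stands, and is why the raw values must stay in the table.
- **The largest figures come from one band.** Only 0.56–0.64 m² is dosed 4 days a week. Phase 1 accumulation CVs of 41% to 107% (on a different, 4-hour definition) exceed most of the schedule effect. This limits the size. It does not remove the systematic difference.
- **Subgroups are tiny.** Eighteen mandatory children over four schedules average 4.5 each, and grouping by days per week would still mix 24 h and 48 h troughs. This stands and shapes the fix.

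Pooling is itself an inference from silence, since Section 9.6 does not forbid grouping. But the section sets out how the analysis will proceed precisely because PK can be presented in several ways, so the omission matters.

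**Conclusion.** The point holds as a limited one. Followed as written, Section 9.6(1) mixes Day 1 exposures from doses of 36 to 71 mg/m² and accumulation ratios whose expected values differ by schedule alone, up to 1.70-fold (4.48/2.63) at 66.2 h.

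It would be tempting to say that the summaries mainly reflect the BSA band, or that accumulation is 41% too low in children not dosed daily. Neither is supported. Dose accounts for roughly a fifth to a quarter of log-AUC variance in small children under assumed BSA ranges and proportionality. The 41% applies to one band; the figures for 5 and 6 days are 24% and 13%. Tmax should not depend on dose under linear kinetics.

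The accumulation part is the firmer half: it needs linear kinetics but hardly depends on the half-life chosen. The AUC and Cmax part also needs dose proportionality, which phase 1 leaves unsettled. What is affected is a set of descriptive summaries serving secondary aim 1.2.2.

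**What to change.** Amend Section 9.6(1) as follows.

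- Report the Day 1 dose in mg/m². Give AUC(0-24h) and Cmax normalised to it beside the raw values, with a note that normalisation assumes dose proportionality and that the phase 1 data leave this open.
- Do not pool the raw accumulation ratio across schedules. Show it by weekly schedule, or daily versus non-daily if numbers are small, with the actual time since the last dose.
- Take the summary accumulation for daily dosing from the population model already planned in Section 9.6(2), using the recorded dosing history.

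The cost is a few lines of SAP wording and slightly more analysis. Doses and dates are already collected in the patient diary (Appendix III) and at PK sampling (Section 7.2.1). No dose, schedule or sample changes. The downside is small, imprecise subgroups.

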**9.7 Gender and Minority Accrual Estimates**

The gender and minority distribution of the study population is expected to be:

Racial Categories	Ethnic Categories				Total
	Not Hispanic or Latino		Hispanic or Latino		
	Female	Male	Female	Male	
American Indian/ Alaska Native		1			1
Asian	2	4			6
Native Hawaiian or Other Pacific Islander					
Black or African American	4	17			21
White	47	44	8	19	118
More Than One Race					
Total	53	66	8	19	146

This distribution was derived from the patients on ADVL0821, ADVL0921, and AOST1521 with diagnoses among the primary disease groups.

**9.8 Analysis of the Pharmacokinetic Parameters**

PK will be required in the first 18 patients less than 9 years of age, then not done on the remaining patients in this age group. PK will be optional for all patients 9–18 years old. PK will not be done in patients older than 18.

The clearance will be measured in the 2–8-year-olds (<9 year olds) and compared to historical data from ADVL1211. The test will be a one-sample equivalence test (using the two one-sided test (TOST) methodology of Schuirmann) of log(Clearance) compared to the historical data with mean 7.584 and standard deviation 0.383 on the log scale. The lower and upper equivalence boundaries will be 60% and 140%, respectively (–0.512 and 0.336 on the log scale). Equivalence will be declared if the two-sided 95% confidence interval on the log scale is entirely contained within the interval (–0.512, 0.336). The power of the test for various combinations of the true population mean and standard deviation in the 2–8-year-old population are displayed below.

Power for sample size $n = 18$				
Ratio of means on raw scale	Difference of means on log scale	Actual variability on log scale ( $\sigma_0 = 0.383$ )		
		$\sigma_0$	$1.25\sigma_0$	$1.5\sigma_0$
0.90	–0.105	98.5%	88.2%	67.3%
0.95	–0.051	97.8%	86.7%	66.0%
1.00	0.000	93.9%	79.1%	59.2%
1.05	0.049	84.8%	66.3%	48.7%

1.10	0.095	69.4%	50.5%	36.6%
------	-------	-------	-------	-------

If the true population mean and standard deviation are identical to the historical data (i.e., ratio of means on raw scale = 1 and actual variability on log scale =  $\sigma_0 = 0.383$ ), the test will have 93.9% power to declare equivalence. If the true population mean is equal to the historical data, the test will still have 79.1% power to declare equivalence if the variability on the log scale is 25% higher than expected and 59.2% power if the variability on the log scale is 50% higher than expected.

If the trial is closed prior to enrolling 18 patients less than 9 years of age, the PK analysis will be done on just the enrolled patients.

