### 2.4.2 Pharmacology/Pharmacokinetics/Correlative Biological Studies

Pharmacokinetics of XL184 were evaluated in the COG/Pilot Consortium phase 1 trial (ADV1211). A preliminary (October 2014) pharmacokinetic analysis was performed using available plasma concentration data from 37 subjects enrolled in ongoing study XL184-011 (ADV1211). Steady state pharmacokinetics were analyzed in 32 patients where full set of samples were available on Cycle 1 day 22. Drug exposure (AUC) was similar for the 3 dose levels (30 mg/m^2, 40 mg/m^2, and 55 mg/m^2) evaluated with no dose proportional increase in exposure. The peak concentration (Cmax) was also similar across the 3 doses levels. The BSA-normalized oral clearance appeared to be similar across the dose levels with a mean ± SD value of 1649 ± 754 L/h/m^2 for all patients. BSA-normalized Cl/F values were similar in females and males (1539 ± 547 L/h/m^2 versus 1835 ± 940 L/h/m^2), and were higher in children ages 12 or younger compared to older children (1889 ± 828 L/h/m^2 versus 1533 ± 694 L/h/m^2); however, this did not reach statistical significance (p value 0.31, Wilcoxon rank sum test). Since the elimination half-life could not be calculated for most patients, an accumulation

ratio was calculated from the plasma concentrations measured 4 hours after drug administration on day 1 and day 21. The half-life was then calculated from this value. The accumulation ratio was  $4.3 \pm 3.9$  and the half-life was  $66.2 \pm 64.7$  hours. Estimates of the cabozantinib pharmacokinetic parameters are summarized below:

Dose Level	30 mg/m  /d	40 mg/m  /d	55 mg/m  /d
N	6	16	10
C max , ng/ml	2025 ± 658 (32%)	1693 ± 692 (41%)	2389 ± 802 (34%)
T max , h	5.24 ± 8.93 (170%)	7.38 ± 8.46 (115%)	4.7 ± 6.57 (140%)
AUC 0-24h , h*ng/ml	32216 ± 8022 (25%)	30010 ± 10985 (37%)	38101 ± 12785 (34%)
Cl/f, ml/h	1621 ± 430 (26%)	2210 ± 857 (39%)	2307 ± 1045 (45%)
Cl/f/m  , ml/h	1140 ± 357 (31%)	1809 ± 872 (48%)	1790 ± 638 (36%)
Accumulation Ratio C 4hr,day21 / C 4hr,day1	5.25 ± 2.17 (41%)	4.72 ± 5.06 (107%)	2.82 ± 1.23 (44%)
Accumulation Adjusted t 1/2 , h	78.7 ± 36.3 (46%)	79.1 ± 86.3 (109%)	37.8 ± 20.8 (55%)

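### Section 9.8 does not say whether clearance is absolute or per m²; its reference value appears to be absolute CL/F, so a ratio of 1.00 need not mean equal clearance per m²

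*Combined protocol and SAP*

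**What the plan says.** Section 9.8 plans a one-sample equivalence test (two one-sided tests) in the first 18 patients under 9 years. The tested variable is "log(Clearance) compared to the historical data with mean 7.584 and standard deviation 0.383 on the log scale". The limits are 60% and 140% (−0.512 and 0.336 on the log scale), and equivalence requires the two-sided 95% confidence interval to lie inside them. Power is 93.9% under the base case, described as "ratio of means on raw scale = 1 and actual variability on log scale" equal to the historical SD. The section gives no units and does not say whether clearance is divided by BSA.

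Section 9.6 does not settle the scale. Its list, "Parameters to be collected are: AUC (0-24h" and onward, covers AUC, peak concentration, time to peak and accumulation, but not clearance. Its population PK analysis is meant "to evaluate the effect of age on the clearance of XL184", again with no scale.

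Section 2.4.2 reports ADVL1211 clearance both ways, as Cl/f and as Cl/f/m². Its narrative comparisons by dose, sex and age all use the BSA-normalized value: "The BSA-normalized oral clearance appeared to be similar across the dose levels with a mean ± SD value of 1649 ± 754" overall, and values that "were higher in children ages 12 or younger compared to older children (1889 ± 828" and so on. The data are an early cut: "A preliminary (October 2014) pharmacokinetic analysis was performed using available plasma concentration data from 37 subjects", of whom 32 had full steady-state sampling.

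Section 4.1 sets the dosing basis: "Dosing will be performed based on body surface area (BSA", at 40 mg/m²/day.

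**The concern.** ADVL1211 offers two clearance scales, and Section 9.8 names neither. The choice matters most in this comparison, because a 2–8-year-old group is set against a reference that also includes older and larger patients. Absolute clearance carries body size with it; clearance per m² largely removes it. Because the drug is dosed per m², the per-m² scale is the one on which no age difference would naturally be read.

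If the reference is absolute, body size is mixed into the equivalence conclusion. Children with the same per-m² clearance could fail the test because they are small, and children with clearly higher per-m² clearance could pass. If an analyst instead computes per-m² clearance and compares it with 7.584, the two sides are on different scales.

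**Working it through.** **1. Reproduce the plan's power.** Inputs from Section 9.8: n = 18, SD 0.383, limits (−0.512, 0.336), two-sided 95% interval, so t(0.975, 17) = 2.110 and the standard error is 0.383/√18 = 0.0903. Equivalence is declared when the mean difference ± 2.110·s/√18 lies inside the limits. Integrating over the chi-square distribution of the sample SD s gives:

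| True ratio 1.00 | SD 0.383 | 1.25 × SD | 1.5 × SD |
|---|---|---|---|
| Printed | 93.9% | 79.1% | 59.2% |
| Recomputed | 93.8% | 79.1% | 59.3% |

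All 15 printed cells agree within 2 points; the largest gap is at ratio 1.10 (69.4% printed, 71.0% recomputed). The table is right for the inputs it uses.

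**2. Which scale does 7.584 sit on?** exp(7.584) = 1966. A mean of logs cannot exceed the log of the arithmetic mean. The largest per-m² mean in Section 2.4.2 is 1889 (age 12 or younger), and ln 1889 = 7.544 < 7.584. So 7.584 is not the log mean of any per-m² group reported there. This step needs no distributional assumption.

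Next, assume log-normality in each dose group: σ² = ln(1 + (SD/mean)²), μ = ln(mean) − σ²/2, weighted by n = 6, 16 and 10.

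| ADVL1211 group | Cl/f, ml/h | μ | Cl/f/m² | μ |
|---|---|---|---|---|
| 30 mg/m² (6) | 1621 ± 430 | 7.357 | 1140 ± 357 | 6.992 |
| 40 mg/m² (16) | 2210 ± 857 | 7.631 | 1809 ± 872 | 7.396 |
| 55 mg/m² (10) | 2307 ± 1045 | 7.650 | 1790 ± 638 | 7.430 |
| Pooled (unrounded μ) | | 7.585 | | 7.331 |

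The pooled total SD is 0.381 for Cl/f and 0.422 for Cl/f/m². The narrative per-m² figure of 1649 ± 754 converts to 7.313 with SD 0.436. Across pooling methods the absolute log mean is 7.585–7.586 with SD about 0.38–0.40, and the per-m² log mean is 7.31–7.33 with SD 0.40–0.44. The mean carries the inference; the SD adds little.

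**3. If absolute clearance is tested.** Absolute CL/F = (CL/F per m²) × BSA. Let k be the children's mean BSA divided by that of ADVL1211, and r the true per-m² ratio. The tested ratio is then about r·k. With n = 18 and SD held at 0.383:

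| k (assumed) | Tested ratio, r = 1 | Declared equivalent | Tested ratio, r = 1.5 | Declared equivalent |
|---|---|---|---|---|
| 0.6 | 0.60 | 3% | 0.90 | 98% |
| 0.7 | 0.70 | 37% | 1.05 | 85% |
| 0.8 | 0.80 | 85% | 1.20 | 36% |
| 0.9 | 0.90 | 98% | 1.35 | 6% |
| 1.0 | 1.00 | 94% | 1.50 | 0.4% |

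The r = 1 column peaks near 0.9 because the log limits are centred at (−0.512 + 0.336)/2 = −0.088. For orientation, the pooled means 2130/1678 imply an ADVL1211 BSA of roughly 1.27 m², so k = 0.6 and k = 0.8 correspond to a child mean of about 0.76 and 1.02 m².

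**4. If per-m² data are compared with 7.584.** With equal per-m² clearance the apparent ratio is exp(7.331 − 7.584) = 0.78 or exp(7.313 − 7.584) = 0.76. Power is 77% and 71% at SD 0.383, and 69% and 60% at SDs 0.422 and 0.436.

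**5. Per m² on both sides.** At ratio 1.00 and n = 18, power is 88.7% (SD 0.422) or 86.5% (SD 0.436).

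**The case against.** The strongest reply is that only the missing definition is established. The scale is inferred from an October 2014 cut with 32 patients at steady state, while Section 2.4.1 reports 41 enrolled. Section 9.8 says only that the reference comes from ADVL1211, so another subset could have supplied it. This stands, and it is why the conclusion is conditional. The SD match is weak evidence by itself: by the same conversion, single per-m² groups run from 0.306 to 0.483, a range that contains 0.383.

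The size also rests on k, which the documents do not give, and on one SD for every k, although absolute clearance in a narrow age band may vary differently. The probabilities therefore show sensitivity to body size, not a measured error.

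A reader might go further and restate the 60–140% limits as limits on drug exposure. The documents do not support this. It would need the same mg/m² dose on both sides, whereas the ADVL1211 patients received 30, 40 or 55 mg/m², and Section 2.4.2 reports no dose-proportional increase in exposure. Per-m² clearance was 1140 at the lowest dose and about 1800 at the other two, so even a pooled per-m² reference mixes dose levels.

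Finally, this is a secondary aim. Section 9.8 ties no decision to the result, and Section 9.6 plans a separate population PK test of age. That limits the stakes, but it does not tell the analyst which clearance to compute.

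**Conclusion.** The point holds in conditional form. Section 9.8 leaves its tested variable undefined, and the reference 7.584/0.383 appears to be absolute CL/F in ml/h. Followed as written, either reading can mislead. Absolute clearance makes the result depend on body size: for equal per-m² clearance, 3% to 98% over k = 0.6 to 1.0; for a 1.5-fold per-m² clearance, 98% down to 0.4%. Per-m² clearance against 7.584 turns no difference into a ratio of 0.76–0.78, with power of about 60–77%. Under the absolute reading, ratio 1.00 means equal per-m² clearance only if the children's mean BSA equals that of ADVL1211.

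Two stronger conclusions are tempting and unsupported. The power table is not wrong, since it reproduces. Nor is the absolute scale proven, since the source of 7.584 is not stated. The figures rest on log-normal conversion of published summaries, on assumed values of k and, in the k table, on a fixed SD of 0.383. No primary decision is affected.

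**What to change.** In Section 9.8:

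- Define the variable as CL/F per m² (ml/h/m²) for both the new data and the reference.
- Replace 7.584/0.383 with the mean and SD of log CL/F per m² computed from ADVL1211 individual data. The summaries in Section 2.4.2 are not a safe source: the dose-group table averages 1678, against 1649 in the text, and the text prints L/h/m² where the table prints ml/h. Those units should be made to agree.
- State which ADVL1211 dose levels the reference pools.
- Recompute the power table. Provisionally, power at ratio 1.00 with n = 18 and SD 0.42–0.44 is 87–89%, in place of 93.9%.

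If absolute CL/F is truly intended, say so, give the units, and state that equivalence does not mean equal clearance per m².

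The cost is wording, one reference value from existing data and one recomputed table, with no new patients or samples. The downside is a somewhat lower stated power.
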